### 1.3 Secondary Study Endpoints

During the first 15 minutes following anesthetic induction:

- (1) The total number of doses of vasopressors (ephedrine, phenylephrine or vasopressin) administered
- (2) Duration of each hypotension episode
- (3) Refractory hypotension (defined as systolic blood pressure <85mm Hg following 3 doses of vasopressors)
- (4) Systolic blood pressure (at 1 minute intervals)
- (5) Diastolic blood pressure (at 1 minute intervals)
- (6) Heart rate (at 1 minute intervals)
- (7) Blood levels of AVP, All, Epi, NE (at 3, 5, 10 and 15 min)

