### **Both groups**

Following induction in both groups, the blood pressure and heart rate will be measured every one minute for the first 15minutes following the administration of either propofol or methohexitol, and all hemodynamic parameters (systolic blood pressure, diastolic blood pressure, heart rate) will be recorded on the data collection sheet.

Hypotension will be defined as a systolic blood pressure of less than 85 mmHg or greater than 30% decrease in the mean systolic blood pressure (as determined above), whichever is greater. If the patient develops hypotension with a systolic blood pressure of less than 85mm Hg during the 15 minutes following induction of anesthesia, the treatment algorithm outlined below will be followed (Eyraud et al., 1999; Mets, 2013):

One dose of phenylephrine will be administered if heart rate is 60 bpm or above, whereas 5mg of ephedrine will be administered if heart rate is below 60 bpm. The blood pressure will be rechecked 1 minute following, and the process repeated once or twice if necessary. If the

patient is still hypotensive following 3 total doses of vasopressors (phenylephrine and/or ephedrine), they will be considered to be in refractory hypotension and 0.5 Units of vasopressin will be administered. The blood pressure will be rechecked 1 minute following administration of vasopressin. If systolic blood pressure is still less than 85 mmHg, an additional 0.5 Units of vasopressin will be repeated once or twice as needed. Persistent refractory hypotension despite the aforementioned vasopressors will be treated with 4 micrograms of intravenous norepinephrine. All hemodynamic parameters for 15min following anesthetic induction will be recorded by the attending anesthesiologist.

Following anesthetic induction in both study groups, blood samples will be collected (as described above) at 3, 5, 10 and 15 minutes following anesthesia induction. The blood samples will be processed by dedicated research technician as described below.

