## 8.2 Sample size determination

The primary outcome of this two-arm trial is the proportion of subjects that have at least one hypotension episode within 15 minutes of administration of the randomized treatment medication. A hypotension episode is defined as having a drop in systolic blood pressure  $>30\%$  from baseline and/or having systolic blood pressure  $<85$  mmHg. Eyraud et al found 42 out of 51 subjects (0.82) had at least one hypotension episode using propofol (Eyraud et al., 1999). We expect our propofol proportion to be slightly higher due to our definition of a hypotension episode and our patient population. Further, we believe an absolute reduction of 0.30 in the proportion of subjects having at least one hypotension episode in the methohexitol group compared to the propofol group is clinically important. Although the randomization will be stratified by two factors (gender and drug type), to provide a conservative sample size estimate these factors were not taken into consideration for the power analysis because the correlation of these stratification covariates with the outcome would simply increase the precision, and hence, increase the power.

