## 8.3 Statistical methods

Primary analyses will invoke an intent-to-treat paradigm, wherein all randomized subjects are included according to their randomized treatment arm, regardless of actual treatment received, compliance, etc. Data will be summarized using descriptive statistics for continuous variables (mean, standard deviation, number of observations, and percentiles) and frequency statistics (frequencies and percentages) for categorical variables. Univariate and bivariate distributions will be inspected in order to address any missing data, inconsistent responses, outliers, and data entry errors. The sample size estimates have taken into consideration a participant drop-out of 20%; however, every effort will be made during the studies to minimize any drop-out. All hypothesis tests will be two-sided and analyses will account for the two randomization stratification factors of gender and inhibitor type. All analyses will be performed using SAS software, version 9.4 (SAS Institute, Inc., Cary, NC), R software, version 3.2.2 (R Foundation for Statistical Computing, Vienna, Austria), or Stata software, version 13 (StataCorp LP, College Station, TX).

For the primary outcome of the proportion of participants having at least one hypotension episode, log-binomial regression will be used to compare the propofol and methohexitol groups, adjusting for the randomization stratification factors of gender and inhibitor type. Because this is a prospective study, the log-binomial model allows us to estimate the risk ratio rather than the odds ratio while adjusting for covariates (Wacholder, 1986).

For secondary outcome of the proportion of patients experiencing refractory hypotension, the log-binomial model as described for the primary outcome will be used to compare the treatment groups. Poisson regression will be used to compare the two treatment groups, adjusting for the randomization stratification factors, with respect to the secondary outcomes of (a) the number of vasopressor doses (i.e., ephedrine, phenylephrine and vasopressin) administered per patient and (b) the number of hypotension episodes per patient over the first 18 after treatment initiation. In the event that there is an excess of zero counts, zero-inflated Poisson (ZIP) regression will be considered (Lambert, 1992).

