For secondary hemodynamic outcomes of systolic blood pressure, diastolic blood pressure and heart rate over the first 15 minutes after treatment initiation, the area under the curve (AUC) for each of these variables will be calculated using the trapezoidal rule. The AUC of each of these variables will be compared between the two treatment groups using linear regression models adjusting for the randomization stratification factors. A linear regression model also will be used to assess differences between the two treatment groups with respect to the duration (in minutes) of hypotension.

Blood will be collected at baseline, 3 min, 5 min, 10 min, and 15 min after treatment initiation to assess changes from baseline in AVP, AI, Epi and NE between the two treatment groups. For these continuous secondary outcomes collected longitudinally, linear mixed-effects models will be fit to compare the two treatment arms with respect to changes in these outcomes over time(Laird and Ware, 1982). The independent variables in the model will be treatment arm, time, the interaction of treatment and time, as well as the randomization stratification factors as covariates. From the mixed-effects models, contrasts will be constructed to test the hypotheses of interest with respect to changes over time in the outcomes. Linear mixed-effects models are an extension of ordinary regression models that account for the between- and within-subject correlation inherent in data involving repeated measurements per subject and allows for the variance-covariance matrix to be explicitly defined.

Following our assessment of the initial fit of the models, we will add covariates to the models that correspond to potential confounders to assess their impact, if any, on the treatment effects. Residual diagnostics will be assessed to determine the appropriateness of the model fit and, if necessary, transformations of the response will be used to meet modeling assumptions. Differences in means and associated confidence intervals (CIs) will be used to quantify the magnitude of the effects for continuous outcomes.

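### The duration analysis states no unit, no population and no value for patients without an episode; read literally, it compares only patients who became hypotensive

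*Combined protocol and SAP*

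**What the plan says.** Section 1.3 gives the only definition of this secondary endpoint, as item (2): "Duration of each hypotension episode". The analysis in section 8.3 is one sentence, which plans a linear regression to "assess differences between the two treatment groups with respect to the duration (in minutes) of hypotension". It names no unit of analysis, no population, no value for a patient without an episode and no handling of a patient with several.

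Other parts of section 8.3 bear on the reading:

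- For the primary analyses, "all randomized subjects are included according to their randomized treatment arm".
- Vasopressor doses and number of episodes are explicitly analysed per patient. For these counts, "In the event that there is an excess of zero counts, zero-inflated Poisson (ZIP) regression will be considered". The duration sentence has no matching provision.
- Mixed models are planned for the neurohormones, which are measured repeatedly. Duration gets linear regression only.
- Transforming the response is allowed if residual diagnostics call for it.

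Under the heading Both groups in section 7.2.2, "the blood pressure and heart rate will be measured every one minute for the first 15minutes", so a total for each patient can be derived from data already collected.

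**The concern.** An endpoint defined per episode has no value for a patient who had no episode. If section 8.3 is applied to that endpoint as worded, the comparison is confined to hypotensive patients. Membership of that group is the primary outcome itself, which the drugs are expected to change, so the two groups compared are no longer the randomised ones. If methohexitol mainly prevents the mildest episodes, its remaining hypotensive patients are the more severe ones, and it can look worse on duration while reducing hypotensive time overall.

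A patient with several episodes would also supply several correlated rows, which ordinary linear regression treats as independent. The plan expects this situation, since it counts episodes per patient.

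The treatment is not blinded (section 7.4.5). If the wording stays open, the choice between readings may be made by people who know the allocation and have seen the data.

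**Working it through.** **Inputs.** From section 8.2: "42 out of 51 subjects (0.82) had at least one hypotension episode using propofol"; "We expect our propofol proportion to be slightly higher", with no figure given; and an absolute reduction of 0.30 on methohexitol. From section 8.1: 47 per group for 90% power, two-sided 0.05, chi-square test; 20% drop-out; 60 per arm enrolled. The documents give no mean, standard deviation or distribution for duration, so every duration below is an assumption.

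**Step 1: reproduce the plan's figure and fix the rates.** With pooled variance and no continuity correction,

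n = [1.96·√(2·p̄·(1−p̄)) + 1.2816·√(pP(1−pP) + pM(1−pM))]² / 0.30².

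For 0.85 vs 0.55, p̄ = 0.70 and n = (1.270 + 0.785)² / 0.09 = 46.9, so 47 per group, as stated. The cited 0.82 (vs 0.52) gives 50 and 0.88 (vs 0.58) gives 44. A propofol rate of 0.85 therefore fits both the 47 and the remark that the rate should be slightly higher. For drop-out, 47/0.8 = 58.75, or 59 per arm; the plan enrols 60.

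**Step 2: patients without an episode, per 60.**

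| Rates (propofol, methohexitol) | Propofol left out | Methohexitol left out |
|---|---|---|
| 0.82, 0.52 | 60 × 0.18 = 10.8 | 60 × 0.48 = 28.8 |
| 0.85, 0.55 | 60 × 0.15 = 9 | 60 × 0.45 = 27 |
| 0.88, 0.58 | 60 × 0.12 = 7.2 | 60 × 0.42 = 25.2 |

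At 0.85 and 0.55, a hypotensive-only analysis compares 51 with 33 patients. It omits 36 of 120 (30%), in a ratio of 1 to 3 by arm.

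**Step 3: when the two analyses disagree.** Let mP and mM be the mean total minutes among hypotensive patients, and r = mM/mP. (This equals the per-episode mean if each hypotensive patient has one episode.)

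- Hypotensive-only difference (methohexitol minus propofol): mP·(r − 1), positive when r > 1.
- All-patient difference: pM·mM − pP·mP = mP·(pM·r − pP), negative when r < pP/pM.

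The signs are opposite when 1 < r < pP/pM. The upper limit is 0.85/0.55 = 1.55, with a range of 0.88/0.58 = 1.52 to 0.82/0.52 = 1.58.

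**Step 4: an example of the mechanism.** Suppose 25% of patients in each arm have 7 hypotensive minutes, and methohexitol removes only 2-minute cases.

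- All patients: propofol 0.60×2 + 0.25×7 = 2.95 min; methohexitol 0.30×2 + 0.25×7 = 2.35 min. Methohexitol is better.
- Hypotensive only: 2.95/0.85 = 3.47 min; 2.35/0.55 = 4.27 min. Methohexitol looks worse (r = 1.23).

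**Step 5: how far this depends on the assumption.** Latent severity was simulated with cut-offs set to give 0.85 and 0.55, and durations capped at 15 minutes. Mean minutes, propofol vs methohexitol:

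| Severity model | Assumed effect | Hypotensive only | All patients |
|---|---|---|---|
| Exponential | prevents mildest cases | 5.52 vs 7.53 | 4.69 vs 4.14 |
| Lognormal | prevents mildest cases | 5.44 vs 7.09 | 4.63 vs 3.90 |
| Normal | prevents mildest cases | 5.82 vs 7.16 | 4.95 vs 3.94 |
| Exponential | shifts severity in all | 4.75 vs 4.75 | 4.04 vs 2.61 |
| Lognormal | shifts severity in all | 3.91 vs 3.95 | 3.32 vs 2.17 |
| Normal | shifts severity in all | 3.93 vs 2.54 | 3.34 vs 1.39 |

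The hypotensive-only comparison reverses under the first type of effect. Under the second it is close to zero or keeps the correct sign. The all-patient comparison favours methohexitol in all six rows.

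**The case against.** The strongest reply is that nothing in section 8.3 restricts the regression to hypotensive patients. The sentence speaks of duration in the singular, without the per-episode wording of section 1.3. It follows directly on the per-patient AUC regressions and is linked to them. The related counts keep their zeros. Where the plan foresees repeated values it uses mixed models, which suggests that one value per patient was intended here. A total with zeros is therefore a fair reading. That stands: a reader might infer that the plan prescribes a hypotensive-only comparison, and the documents do not go that far.

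The reply does not settle the matter. The all-randomised statement is worded for the primary analyses and cannot assign a number to an endpoint that is undefined without an episode. The per-patient wording and the provision for zeros are given for the counts and are absent for duration. Even under the favourable reading, about 30% of values would be zero at the planning rates. The permitted transformation, if a logarithm, would remove those patients and bring the subgroup back.

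It can also be said that the systolic pressure AUC already gives a comparison that does not condition on becoming hypotensive, and that this is one of seven secondary endpoints. Both are true. They limit the consequence without defining the duration analysis.

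**Conclusion.** The concern holds as a gap in definition with a harmful literal reading. The unit, summary and population of the duration analysis are unspecified. The only endpoint definition, followed as written, leads to a comparison of groups selected by the primary outcome, with repeated episodes counted as independent. At 0.85 vs 0.55 it would omit about 9 and 27 of 60 patients, and its sign would oppose the all-patient result for any r between 1 and about 1.55 (1.52 to 1.58 over the range of rates).

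A reader might go further and infer that the sign will reverse, or that an all-patient analysis brings a particular gain in power. The documents support neither, because both depend on a duration distribution that is not given. Nor does the point reach the primary outcome, its log-binomial analysis or the sample size. It should be corrected before analysis, at the level of a secondary endpoint.

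**What to change.** In sections 1.3 and 8.3, define the outcome as total minutes of hypotension in the first 15 minutes for every randomised patient, zero if none, derived from the one-minute readings. Reserve zero for patients whose readings show no hypotension; missing readings need their own stated rule.

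Use the primary-endpoint definition of hypotension, once its wording is reconciled. Sections 1.2 and 8.2 join the relative fall and the 85 mmHg limit by and/or, while the Both groups text in section 7.2.2 points to the larger of the two.

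Compare mean minutes between arms with the stratum-adjusted linear regression already planned, using robust standard errors, and rule out a log transformation that would drop the zeros. Report episode length among hypotensive patients descriptively only, with no test between arms.

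The cost is a small change of wording and no new data. The drawback is a skewed, bounded outcome with many zeros, which is why robust standard errors are needed.

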#### **7.2.3 Following sample collection from several patients**

At a later time, after samples have been collected from several study participants, serum samples will be processed to quantify Angiotensin II and plasma samples for Arginine Vasopressin, Epinephrine, and Norepinephrine using commercially available kits. Angiotensin II concentration will be determined using RayBiotech Human AngII EIA (EIA-AngII). Other markers will be measured using ELISA kits from Abnova; Arg8-Vasopressin ELISA (KA0301), Epinephrine ELISA (KA1882), and Norepinephrine (KA1891). Samples will be processed according to manufacturer's instructions.

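### AVP and norepinephrine samples drawn after rescue with those same hormones enter the mixed models with no stated handling, so late contrasts can mix injected drug with the induction agent's effect (minor)

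*Combined protocol and SAP*

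**What the plan says.** Specific Aim 2 (section 1.1) asks how the two induction drugs affect circulating AVP, angiotensin II, norepinephrine and epinephrine. Section 1.3 lists the blood levels of these hormones as the seventh secondary endpoint.

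In section 7.2.2 (Both groups), a patient whose pressure stays low after three doses of phenylephrine and/or ephedrine is handled as follows: "they will be considered to be in refractory hypotension and 0.5 Units of vasopressin will be administered". Vasopressin may be repeated once or twice, and hypotension that still persists "will be treated with 4 micrograms of intravenous norepinephrine". All this falls in the 15 minutes after induction, when blood is also drawn at 3, 5, 10 and 15 minutes.

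Section 7.2.3 processes "plasma samples for Arginine Vasopressin, Epinephrine, and Norepinephrine using commercially available kits".

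In section 8.3, for these hormones, "linear mixed-effects models will be fit to compare the two treatment arms with respect to changes in these outcomes over time". "The independent variables in the model will be treatment arm, time, the interaction of treatment and time", plus the stratification factors. The section notes that this class of model "allows for the variance-covariance matrix to be explicitly defined". It also plans residual diagnostics, transformations, and later covariates that it does not name. On data quality it says: "Univariate and bivariate distributions will be inspected in order to address any missing data, inconsistent responses, outliers, and data entry errors".

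For the data collection sheet, section 7.2.2 says that "all hemodynamic parameters (systolic blood pressure, diastolic blood pressure, heart rate) will be recorded on the data collection sheet"; dose times are not mentioned there. Section 10.2 shows that vasopressor type and dosage are held in REDCap.

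**The concern.** Two rescue drugs are the same substances as two of the measured outcomes. An AVP value after injected vasopressin, or a norepinephrine value after injected norepinephrine, may reflect the syringe as well as the patient. The models take such values like any other.

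The trial's hypothesis is deeper hypotension with propofol, and section 8.2 targets a 0.30 absolute difference in the proportion with any hypotension. Rescue may therefore be more common in one arm. A late arm difference in AVP or norepinephrine could then come partly from rescue dosing and be reported as an effect of the induction agent on the patient's own hormone response. Even with equal rescue, a few very high values would inflate the variance and could hide a real difference.

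**Working it through.** **1. Can injected drug precede a sample?** Let the run of readings below 85 mmHg start at minute m, with each dose given at its reading and a recheck one minute later, as section 7.2.2 describes.

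- The three initial vasopressor doses fall at m, m+1 and m+2, so vasopressin falls at m+3.
- Vasopressin is repeated once or twice (m+4, m+5), so norepinephrine falls at m+5 or m+6.
- Vasopressin precedes the sample at time s if m+3 < s. This gives m = 1 for 5 min, m ≤ 6 for 10 min and m ≤ 11 for 15 min.
- Norepinephrine precedes the sample if m+5 < s or m+6 < s. This gives m ≤ 4 or 3 for 10 min, and m ≤ 9 or 8 for 15 min.
- With readings starting at minute 1, the earliest vasopressin is at minute 4. The baseline and 3-minute samples therefore come before either drug.

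**2. Is there a handling rule elsewhere?**

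- The intent-to-treat sentence in 8.3 covers primary analyses and which subjects are included, not single samples.
- Outlier inspection has no criterion, and a high value after injection is a real measurement.
- Transformation can reduce skew but cannot remove injected drug.
- The later covariates are unnamed, and rescue happens after randomisation.
- The exclusion for protocol non-adherence (end of 7.2.2) does not apply, because rescue follows the protocol.

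**3. How large could it be?** The plan has no figure to reproduce. The illustration takes 47 per arm from section 8.1. Everything else is assumed: the share of patients given vasopressin in each arm, and the rise D that it causes in SD units. The outcome is the 10-minute AVP change from baseline (SD 1), compared by t-test. The added arm difference is (share in propofol − share in methohexitol) × D; for example, (0.17 − 0.11) × 5 = 0.30 SD.

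Without contamination, false positives are 0.050 and power for a true 0.7 SD difference is about 0.92. If every rescued patient is affected by 10 minutes:

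| Shares | D | False positives | Power, true difference opposite to contamination | Power, same direction |
|---|---|---|---|---|
| 1.7% vs 1.1% | 1 | 0.050 | 0.912 | 0.918 |
| 1.7% vs 1.1% | 5 | 0.049 | 0.789 | 0.858 |
| 4.3% vs 2.8% | 5 | 0.054 | 0.607 | 0.783 |
| 17% vs 11% | 1 | 0.059 | 0.827 | 0.930 |
| 17% vs 11% | 2 | 0.077 | 0.630 | 0.898 |
| 17% vs 11% | 5 | 0.111 | 0.168 | 0.671 |
| 14% vs 14% | 5 | 0.050 | 0.392 | 0.391 |

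**4. Applying the timing from step 1.** If onset is uniform over minutes 1 to 11, only 6/11 of rescued patients have had vasopressin before the 10-minute sample. Shares of 17% vs 11% become 17 × 6/11 = 9.3% vs 11 × 6/11 = 6.0%. With D = 5, false positives fall to about 0.072 and opposite-direction power is about 0.36. With D = 2, false positives are about 0.059. If every onset is at minute 6 or earlier, the table stands.

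**5. Would dropping post-rescue samples be unbiased?** Only if rescued patients' own hormone response is like that of the others. If it is E SD higher, removal shifts the arm difference by about (0.17 − 0.11) × E, which is 0.03, 0.06 or 0.12 SD for E = 0.5, 1 or 2. Keeping all samples shifts it by 0.06 × D, which is 0.06, 0.12 or 0.30 SD for D = 1, 2 or 5. Removal is closer to the endogenous difference only when D exceeds E, and the documents give neither.

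Norepinephrine was not simulated. It is given only after vasopressin has failed, so its shares cannot exceed those for vasopressin.

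**The case against.** The strongest case against is that the plan may already estimate what it intends. Aim 2 concerns circulating hormones and the endpoint is a blood level. Read literally, that is the total level, which the all-samples model estimates. This stands as a reading: the documents never say that the target is the patient's own hormone. What remains is that the target is not stated, and that attributing a difference to the induction agent needs more than a total level.

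A reader might infer that samples after rescue should be excluded from the main analysis. The documents do not support that. The loss would be informative, and step 5 shows that neither analysis is always closer. An assurance that exclusion keeps false positives at 5% holds only if rescue is unrelated to the patient's own hormone level.

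A reader might also infer serious error inflation, particularly by simulating a random-intercept model with one residual variance and a rise in every late sample. Section 8.3 does not commit to that covariance. Part of the resulting inflation is misspecification, and step 1 shows that not every late sample is exposed. That evidence should not be used.

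The assumed shares have no source. Vasopressin needs a pressure still below 85 mmHg after three doses, which is much narrower than the primary endpoint. At 1.7% vs 1.1% the false-positive effect is nil, and the chance that nobody in either arm receives vasopressin is 0.983^47 × 0.989^47, about 27%. This objection to the size stands.

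Finally, REDCap already holds vasopressor type and dosage, so patients given either drug can be identified; only dose timing is uncertain. The collection sheet itself is not among the documents.

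**Conclusion.** The gap is real and minor. Run as written, the late AVP and norepinephrine contrasts can mix injected drug with the effect of the induction agent, possibly unequally by arm, and no provision addresses this. It is confined to AVP from 5 minutes and norepinephrine from 10 minutes, in patients who reach the later rescue steps, within one secondary endpoint.

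The size is unknown. Under the assumed inputs, false positives at 10 minutes run from about 5% to about 11%, or about 7% at the top with uniform onset. Power loss can be the larger effect, and it occurs even with equal rescue. The conclusion also assumes that the kits detect the injected drug. The documents do not discuss this; it is inferred because the same hormone is given and measured.

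**What to change.** In section 8.3:

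- State whether the AVP and norepinephrine target is the total circulating level or the patient's own response.
- Pre-specify two analyses, reported side by side. One uses all samples. The other sets to missing AVP samples drawn after the first vasopressin dose and norepinephrine samples drawn after the first norepinephrine dose.
- Report the number of affected samples by arm and time.
- Attribute a late AVP or norepinephrine difference to the induction agent's effect on the patient's own hormone only if both analyses agree.
- State that the second analysis loses samples from the most hypotensive patients and relies on missing at random. That is doubtful, because blood pressure triggers rescue and is not in the hormone model.

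Confirm that the time of each vasopressin and norepinephrine dose is recorded, and add the field if it is not.

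The cost is some SAP wording, a little more analysis work and possibly one data field. The two analyses may disagree, in which case the late contrast stays unexplained. Rescue treatment is unchanged.

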applied to the ipsilateral arm. An appropriately-sized blood pressure cuff shall be defined as a cuff whose bladder length is at least 80% of the arm circumference, and whose width covers 2/3 of the distance from the elbow to the shoulder. Blood samples, for baseline analysis of AVP, All, NE and Epi levels, will be collected from the IV as follows: A tourniquet will be applied proximal to the intravenous catheter, following which 3cc of blood will be removed first to clear the 'dead space' in the intravenous line and prevent erroneous blood sampling. This blood will be discarded. A further 10cc of blood will be collected in appropriately labeled tubes (5ml in serum red top vacutainers tubes and 5ml in vacutainers tubes containing EDTA) and kept on ice until processing by our research technician, as described below. Following collection of the blood sample, 5cc of normal saline will be used to flush the line and prevent blood from clotting the catheter. A second IV will also be established in the preoperative area under local anesthesia as described above to administer intravenous medications and fluids intraoperatively according to current anesthetic standards of care.

**Operating Room Procedures:** Subjects will be attached to standard ASA monitors including electrocardiogram and pulse oximetry and noninvasive blood pressure monitor. Baseline blood pressure will be determined by taking three automated successive non-invasive blood pressure measurements every 1-2 minutes, until the systolic blood pressure (SBP) measurements is consistent (difference of no more than 10% between readings) with the patient lying in supine position. The average SBP and accompanying heart rate (HR) of these three measurements will be recorded as mean baseline values.

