#### **7.4.3 Method for Assigning Subject to Treatment Groups**

The randomization scheme for this study will use variable-size, random permuted blocks to ensure that the number of participants in each treatment arm is balanced after each set of  $B$  randomized participants, where  $B$  is the block size. We will use a block size of 10. Furthermore, the randomization will be stratified by gender (male/female) and drug type (ACEI/ARB). Randomization to the propofol or methohexitol arms will use 1:1 allocation. A research coordinator will access the randomization lists (developed through the website Randomization.com) stored in the secure REDCap database to randomize the participant.

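### The hormone model in 8.3 makes no precision-gaining use of the pre-drug baseline sample; stating a common baseline mean would generally sharpen the Aim 2 contrasts at almost no cost

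*Combined protocol and SAP*

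**What the plan says.** Section 8.3 (Statistical methods) sets the target as change from baseline: "Blood will be collected at baseline, 3 min, 5 min, 10 min, and 15 min after treatment initiation to assess changes from baseline". On the fixed effects of the mixed model it says: "The independent variables in the model will be treatment arm, time, the interaction of treatment and time", and it adds the two stratification factors as covariates. For inference, "contrasts will be constructed to test the hypotheses of interest with respect to changes over time in the outcomes", but the contrasts are not written out. On covariance, the section says only that the method "allows for the variance-covariance matrix to be explicitly defined"; no structure is chosen. Whether time enters as categories or as a linear term is not stated.

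After the initial fit, "we will add covariates to the models that correspond to potential confounders". The baseline hormone level is not named among them.

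Two other passages matter. Section 7.2.2 places the baseline draw in the preoperative area, before any study drug: "Blood samples, for baseline analysis of AVP, All, NE and Epi levels, will be collected from the IV as follows". Section 7.4.3 states that "Randomization to the propofol or methohexitol arms will use 1:1 allocation".

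**The concern.** If baseline is one of five modelled visits, a treatment main effect lets each arm have its own baseline mean. Every contrast against baseline then subtracts an estimated baseline difference between arms. Because the sample precedes study drug and allocation is random, that difference has expectation zero, so estimating it mostly adds noise. Using the patient's own baseline level, or equivalently a shared baseline mean, removes that noise.

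At stake is the precision of Specific Aim 2. Sections 8.1 and 8.2 size the trial only for the binary primary endpoint, and no power or precision is given for any hormone. Section 8.2 already accepts the principle for the stratification factors, arguing that covariates related to the outcome raise power. The baseline hormone level is collected anyway and is an obvious candidate for the same treatment.

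**Working it through.** **The plan's own figure.** There is none for the hormones. The only sample-size figure is 47 evaluable patients per arm for the primary endpoint (90% power, two-sided 0.05, difference 0.30). The planned propofol rate is not stated; 0.85 against 0.55 reproduces the figure:

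n = [1.96·√(2·0.70·0.30) + 1.2816·√(0.85·0.15 + 0.55·0.45)]² / 0.30² = (1.270 + 0.785)² / 0.09 = 46.9, so 47.

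I use 47 per arm below only as the n for the hormone contrasts.

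**Inputs.** From the documents: five sampling times, 1:1 allocation, the fixed effects above, baseline drawn before drug. Assumed, because the documents give no value: rho, the correlation between baseline and a given later visit, and k, the later SD divided by the baseline SD. Both apply on the scale finally analysed, since 8.3 allows transformation.

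**Formulas.** In units of baseline variance, with n per arm, categorical time and complete data:

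- Planned contrast (arm-specific baseline means): (2/n)(1 + k² − 2·rho·k). This is the variance of a difference in mean change scores.
- Baseline-adjusted contrast (common baseline mean): (2/n)·k²(1 − rho²).
- Excess of the first over the second: (2/n)(1 − rho·k)², which is never negative and is zero when rho·k = 1.

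The stratification factors do not alter the planned contrast, because they are constant over time.

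**Check of the algebra.** At n = 47, k = 1, rho = 0.5 the formulas give 2/47 = 0.04255 and 1.5/47 = 0.03191. An exact generalised-least-squares calculation with five visits and two stratification covariates returned the same two values. The equality with the change score also held under a correlation that decays between visits. On simulated complete data the model contrast and the simple change difference were identical (0.2365).

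**Results.** The factor 2/n cancels from the ratio.

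| k | rho | planned | adjusted | planned/adjusted | SE reduction |
|---|---|---|---|---|---|
| 0.5 | 0.5 | 0.75 | 0.1875 | 4.00 | 50% |
| 1 | 0.3 | 1.40 | 0.91 | 1.54 | 19% |
| 1 | 0.5 | 1.00 | 0.75 | 1.33 | 13% |
| 1 | 0.7 | 0.60 | 0.51 | 1.18 | 8% |
| 1 | 0.9 | 0.20 | 0.19 | 1.05 | 2.5% |
| 1.5 | 0.3 | 2.35 | 2.0475 | 1.148 | 6.7% |
| 1.5 | 0.5 | 1.75 | 1.6875 | 1.037 | 1.8% |
| 1.5 | 0.7 | 1.15 | 1.1475 | 1.002 | 0.1% |
| 2 | 0.3 | 3.80 | 3.64 | 1.044 | 2.1% |
| 2 | 0.5 | 3.00 | 3.00 | 1.000 | 0% |
| 2 | 0.7 | 2.20 | 2.04 | 1.078 | 3.7% |

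The SE reduction is 1 − √(adjusted/planned); for example, at k = 1 and rho = 0.3, 1 − √0.65 = 0.194.

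**In terms of power.** Take an effect with 80% power under the planned contrast at 47 per arm. With k = 1 its power after adjustment is about 0.935, 0.90 and 0.86 for rho 0.3, 0.5 and 0.7. With k = 1.5, the normal approximation Φ(2.80·√(planned/adjusted) − 1.96) gives about 0.85, 0.81 and 0.80.

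**If time is linear.** The contrast becomes a difference in slopes. With k = 1 and equal correlation between all visits, the variance ratio is 1.49, 1.26 and 1.12 for the same three correlations, so the loss remains but its size changes.

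**The case against.** The strongest reply is that arm, time and arm-by-time is a conventional model that answers the stated question directly. A reader might infer from the concern that the planned hormone results would be biased, or their error rate wrong. The documents do not support that: under randomization the change-score contrast is unbiased with correct type I error. This reply stands in full.

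A second tempting reading is that the plan certainly analyses plain change scores. Section 8.3 does not go that far. Time coding, covariance and contrasts are open, and the identity needs complete data. With about 20% simulated loss of later samples, the model contrast was 0.187 against 0.172 for the simple difference. If only post-induction visits were modelled, the baseline would not be used at all. The statement must therefore be conditional.

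A third is to quote the k = 1 figures as the loss, for example a variance ratio of 1.54 read as 54% more patients. That assumes equal SDs before and after induction, which nothing in the documents establishes. There is reason to doubt it for two analytes: the treatment algorithm in 7.2.2 allows vasopressin and norepinephrine, and both hormones are measured in the later samples. That could push k above 1, where the gain may nearly vanish. This objection also stands, and is why a range is given. Since Aim 2 has no power target, there is also no stated shortfall.

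Finally, 7.2.2 describes randomization before the baseline draw, and 7.4.5 says the drug is not blinded. Equal expected baselines remain a reasonable assumption because no study drug has been given. It is safest when all randomized patients with any sample are kept, since 3.3.1 and 7.2.2 remove some after allocation.

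The option to add unnamed potential confounders after the initial fit does not answer the point: baseline level is not named, and a later addition is not a prespecified analysis.

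**Conclusion.** The point holds as a conditional efficiency improvement. Section 8.3 states no use of the baseline level as a covariate and no common baseline mean. On the natural reading (baseline a modelled visit, categorical time), the contrasts are generally less precise than the collected data allow. The SE reduction available is 8% to 19% at k = 1 with rho from 0.3 to 0.7. It is 0.1% to 6.7% at k = 1.5, nil at rho·k = 1, and greater than the k = 1 values when k is below 1. Rho and k are assumptions and may differ by hormone and by visit. Apart from about one degree of freedom, adjustment is not less precise than the change score in large samples.

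The point is confined to the four secondary hormone outcomes of Aim 2. It does not touch the primary hypotension endpoint or the haemodynamic AUC models.

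**What to change.** Before analysis, replace the open wording in 8.3 with a full specification for each hormone:

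- all five samples as responses, with time as categories;
- one baseline mean shared by both arms, that is, no treatment effect at time 0;
- treatment-by-time terms at 3, 5, 10 and 15 minutes, which are then the treatment contrasts;
- the two stratification factors as now;
- an unstructured covariance matrix.

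An alternative is to model the four post-baseline values with the baseline level and a baseline-by-time interaction as covariates. With complete data this is nearly equivalent. With missing samples the two differ: the constrained model also keeps patients whose baseline is missing, which is relevant given the drop-out of up to 20% allowed for in 8.1.

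The cost is a few lines of model specification and about one degree of freedom. No new data are needed.
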